**NCT02830165**

**Phase I feasibility trial of preoperative adjuvant stereotactic body radiotherapy for patients at high risk of local failure after prostatectomy**

**PRINCIPAL INVESTIGATORS:** [name]., Ph.D.  
**CO - INVESTIGATORS:** Assistant Professor, UCLA Radiation Oncology

[name]., M.D.  
Professor, UCLA Radiation Oncology

[name].  
Professor, UCLA Urology and Molecular Biology

[name].  
Professor & Chair, UCLA Radiation Oncology

[name].  
Assistant Professor, UCLA Radiation Oncology

[name].  
Assistant Professor, UCLA Radiation Oncology

**STUDY COORDINATOR:** [name]  
Study Coordinator, UCLA Radiation Oncology  
[name]  
Study Coordinator, UCLA Urologic Oncology

**STUDY CENTER:** UCLA Jonsson Comprehensive Cancer Center  
Department of Radiation Oncology  
[name],  
[name]

**Clinical Rationale:** Prostate cancer patients with pathologic T3 disease, extensive positive margins, or high gleason grade are at elevated risk of local failure after prostatectomy (1–3). Adjuvant radiation improves clinically meaningful outcomes for patients at high risk of local failure after radical prostatectomy and is a standard of care (2). Adjuvant radiation, typically delivered postoperatively, is clinically underutilized (4). Preoperative adjuvant radiotherapy, if clinically feasible, would be a subject of interest for future clinical trials.

Preoperative adjuvant radiotherapy offers the following additional advantages: (1) reduced radiation dose to normal tissues; (2) lower prescription dose; (3) ability to utilize stereotactic body radiotherapy (SBRT); (4) patient convenience; (5) radiobiologic advantage of high dose per fraction treatment delivery. Furthermore, multiparametric (mp) MRI can predict extraprostatic extension (EPE) and seminal vesicle invasion (SVI) with 90% specificity (4), thereby offering a non-invasive method of selecting patients for preoperative adjuvant radiation. Prior clinical trials have evaluated the safety of, and identified a safe dose for, preoperative radiotherapy in prostate cancer. The feasibility of pre-operative adjuvant radiotherapy has yet to be evaluated.

**Hypothesis:** Preoperative adjuvant radiotherapy delivered by SBRT prior to prostatectomy in patients at high risk of local failure is feasible.

**Design:** This is a single arm Phase I feasibility study in prostate cancer patients at high risk for recurrence after prostatectomy.

- Patients will receive 3 fractions of 8Gy delivered by SBRT over 1-2 weeks, 2-4 weeks prior to prostatectomy and will come to clinic for standard follow-up for one year after surgery.

**Primary Objective:**

To assess feasibility of pre-operative SBRT in prostate cancer patients after prostatectomy. We consider the trial feasible when the estimated treatment completion rate for an enrolled patient is 75%. A patient is considered to have completed treatment if they received the prescribed radiation and undergo prostatectomy within 4 weeks of completing radiotherapy.

**Secondary Objectives:**

To assess acute toxicity (CTCAE v 4.0) and quality of life (EPIC and IPSS)

Correlative molecular analyses of tumor tissue and serum markers in patients that have undergone SBRT

**Translational Significance:** From laboratory studies we already know that the response of prostate cancer cells and tissues to high dose per fraction RT (8 Gy) differs from that to conventional dose per fraction RT (1.8-2 Gy) in ways beyond what can be expected from simple excess tumor cell death alone (6–8). We have evidence that the local and systemic immune responses that may be generated towards radiation- damaged prostate tumors after SBRT may be responsible for the discrepancy (8). However, the very conditions that promote tumor immunity may also enhance radiation- induced reprogramming of cancer towards a stem cell phenotype. How these differing outcomes play out in individual high-risk patients may be critical to the clinical outcome. The correlative analyses of this study will examine the tumor micro-environmental changes that might drive these divergent responses. This trial of prostate SBRT followed by prostatectomy offers a unique translational opportunity to study the radiobiology of SBRT in resected tissues.

**Protocol Overview**

SBRT	Prostatectomy	Tests at each Follow-up
24Gy in 3 fractions (8 Gy per fraction)	Open or robotic assisted prostatectomy within 4 weeks (preferable 2 weeks) of SBRT	CTCAE toxicity scores, QOL-EPIC & IPSS scores, blood (including PSA)

[figure not shown]
Study Design: Prospective Phase I  
 Sample size: 12 patients, single-institutional  
 Outcome: Feasibility assessment (percent of patients completing scheduled treatment)  
 Treatment: SBRT, prostatectomy  
 RT targets: Prostate PTV = prostate and SV (only if involved on MRI or biopsy)

Target Prescription Doses:

Prostate PTV 24 Gy in 3 fractions, 8 Gy per fraction

RT Technique: image-guided SBRT via robotic radiosurgery, IMRT, or VMAT, with daily and intra-fraction Image-guidance (MRI-based, fiducial-based or CBCT-based)

### Trial Flowchart

## **Background**

Prostate cancer is the most common non-cutaneous malignancy in men and second leading cause of cancer death in men (9). There are more than 230,000 incident cases per year and 30,000 deaths in the United States – the vast majority of which are from metastatic castrate resistant prostate cancer. However, more than 90% of men with metastatic prostate cancer are initially diagnosed with localized, not metastatic, prostate cancer. Therefore, improving cancer care for localized prostate cancer that is at high risk for recurrence is likely to reduce mortality.

The standard of care for localized prostate cancer is prostatectomy or definitive radiotherapy ± androgen deprivation therapy (ADT) (10). Patients who undergo surgery and have adverse features of positive margins, EPE, or SVI have up to 45-75% risk of biochemical failure within 5 years. Patients that undergo prostatectomy and have pathologic T stage 3 or greater or positive margins benefit from additional adjuvant therapy (2,3). Three randomized trials demonstrate improved progression free survival with the addition of adjuvant radiotherapy after prostatectomy in patients with pathologic T3 or positive margins: SWOG 8794, EORTC 22911, and ARO 96–02. SWOG 8794 was powered to detect a survival advantage and it did (2). As such, adjuvant radiotherapy with prostatectomy is a standard of care for patients with adverse features of pT3 (EPE or SVI), positive margins, or Gleason Grade 8-10 (2015 NCCN guidelines).

Prostate cancer imaging techniques have advanced such that prostate mp MRI can detect EPE and SVI with 90% specificity (5).

Only 15% of patients who meet the criteria for adjuvant radiation actually undergo this treatment (5). This low utilization may result from the inconvenience associated with seven to eight weeks of daily treatments, toxicity due to normal tissue irradiation, and the possibility that later salvage radiation at PSA recurrence might offer an alternative. The latter is unknown and is the subject of current investigations. The safety of pre-operative adjuvant radiotherapy has been evaluated in clinical trials and a safe biologically effective dose has been identified (12–14). Pre-operative adjuvant radiotherapy, if shown to be feasible, would be a subject of interest for a larger clinical trial.

### **Prior Studies of pre-operative radiotherapy in prostate cancer assessing safety**

Duke University undertook a phase I dose escalation trial of pre-operative fractionated intensity modulated RT followed by prostatectomy (12). All patients were treated to the prostate and seminal vesicles to 39.6, 45, 50.4, and 54 Gy in fractions of 1.8 Gy. The pelvic nodes were also treated, but to a maximal dose of 45 Gy. No intraoperative morbidity was observed. Acute toxicity was limited to Grade 1 (GU and GI). Late toxicity, primarily GU, was within the range expected for adjuvant post-operative RT.

The conclusion was that 54 Gy is a safe dose for preoperative RT followed by prostatectomy.

Princess Margaret Hospital undertook a phase I trial of 15 patients for pre-operative RT followed by prostatectomy within four weeks of completing RT (15, 16). Conformal RT technique (one patient was treated with IMRT) was used to deliver 5 fractions of 5 Gy without image guidance. There were no intraoperative complications, no late GI toxicity. Two cases of long-term urinary incontinence were observed. Overall, GU toxicity was within the range expected for adjuvant post-operative RT.

Notably, our study would utilize modern image guidance and precise treatment volumes, which have been shown to reduce GU and GI toxicity in prostate radiotherapy as compared to conformal techniques.

### **Selection of RT dose for the current study**

The preceding studies evaluating RT prior to prostatectomy demonstrate safety of pre-operative RT at doses of up to 54 Gy in 30 fractions (12). The critical organs at risk in prostate RT are the rectum and bladder. The biological effectiveness of RT for a given physical dose varies between tissues; different tissues (including tumor) are differentially responsive to dose per fraction (quantified by the alpha-beta ratio specific to the tissue or tumor) (15). In the rectum and bladder (alpha-beta ratio of 3-4) (16,17), an RT regimen of 24 Gy delivered in 3 fractions of 8 Gy is biologically equivalent to a dose less than 54 Gy delivered in 30 fractions of 1.8 Gy (the dose previously shown to be safe when delivered to the prostate and seminal vesicles prior to prostatectomy). However, because prostate tumors have a greater sensitivity to changes in dose per fraction than the rectum and bladder (alpha-beta ratio of 1.5) (18, 19), 24 Gy delivered in 3 fractions of 8 Gy deposits a higher biologically effective dose than 54 Gy in 30 fractions in prostate tumor tissue. A dose of 24 Gy delivered in 3 fractions is biologically equivalent in prostate tumor tissue to a standard post-operative adjuvant dose of 70.2 Gy delivered in fractions of 1.8 Gy.

In summary, our selected dose is: 1- based on prior studies identifying a safe dose; and, 2- equivalent to the standard adjuvant RT dose delivered postoperatively. Furthermore, delivering the radiation by SBRT using modern image guidance systems and precise treatment volumes is expected to further reduce toxicity as compared to the prior studies which did not use this delivery technique.

### **Biologic rationale for combination of preoperative adjuvant radiation delivered by SBRT with prostatectomy**

The goal of adjuvant prostate radiotherapy is to eradicate residual disease associated with EPE and positive margins. The target is therefore the prostate surgical bed.

However, precise delineation of the clinical target volume (CTV) of the prostate bed is complicated by changes in anatomy due to surgery. Not surprisingly, controversy exists in the optimal target volume. The CTV must include significant portions of the posterior bladder wall and extend to the anterior rectal wall, exposing normal, healthy tissues to full dose radiation. A standard post-operative adjuvant dose is 70.2 Gy delivered in 39 fractions of 1.8 Gy.

Prostate cancer is highly sensitive to dose per fraction (the prostate cancer alpha-beta ratio of 1.5 is much smaller than 10, which is typical of other malignancies) (15). Consequently, there is a biologic rationale to use fewer, but relatively larger sized fractions (~8 Gy per fraction) of radiation in prostate cancer, compared to conventional fractions of 1.8 to 2 Gy that are used for most cancers (20).

Definitive radiotherapy for prostate cancer has benefited greatly from technical improvements in image guidance and treatment delivery, enabling large fraction sizes to be safely delivered by stereotactic body radiotherapy (SBRT = delivery of up to five fractions with tight margins under image guidance). The CTV for prostate SBRT is the prostate alone (and seminal vesicles if involved) and the planning target volume (PTV) is a small expansion. Unfortunately, the use of SBRT in the postoperative setting (adjuvant or salvage) is frustrated by the lack of consensus of the ideal CTV and the necessity of including significant volumes of normal tissues.

Therefore, there is a two-fold rationale to utilize preoperative, adjuvant SBRT in patients at risk for local failure after prostatectomy: 1- pre-operative RT delivered by SBRT is more convenient for patients (only 3 treatments), which would likely increase utilization of adjuvant RT if shown to be clinically feasible; 2- delivery of large fraction sizes are radiobiologically advantageous.

### **Clinical - Translational Relevance**

Empiric clinical data has demonstrated that prostate adenocarcinoma is exquisitely sensitive to changes in fractional size of radiation dose to a degree larger than even surrounding normal tissues (19, 19). It follows that there is no benefit derived from fractionating radiation dose to the conventional daily dose of 2 Gy during treatment, and that use of larger fractions will increase the therapeutic benefit with more tumor control at the same or decreased toxicity. This is in contrast to most other cancer types where conventional fractionation to 1.8-2 Gy per day is justified because surrounding normal tissues, but not tumors, are spared.

SBRT is the technique of choice to deliver such higher doses. Surprisingly, though, our understanding of the biology behind SBRT have not kept up with the clinical success of this modality due to a dearth of translational studies using specimens from patients treated with SBRT. This Phase I trial of preoperative SBRT in patients at high risk of local recurrence following prostatectomy offers the possibility of studying the radiobiology of SBRT in the clinic. It also lends itself to examination of the role of radiation-

induced immunity in preventing recurrences in high-risk disease and to the role of EMT in promoting recurrences. The dynamic nature of the relationships between these phenomena is of particular interest to our team.

In vitro and in vivo work has suggested that high dose per fraction RT alters the extent and the type of damage to DNA and to vascular structures including endothelial cells, and it seems to generate stronger anti-tumor immunity. We already know that irradiation generates an immunogenic cancer cell death, in part by inducing genetic programs that signal “danger” to the immune system (6). SBRT may therefore drive immune recognition and tumor immunity of potentially systemic proportions (8). It starts with the generation of a pro-inflammatory microenvironment with up-regulation of MHC and co-stimulatory molecules that can enhance tumor antigen cross-presentation by dendritic cells and that broadens the antigenic repertoire. Progenitor cells of mesenchymal, endothelial, myeloid and lymphoid origin get mobilized to infiltrate the irradiated area. What is important here is that according to preclinical evidence, doses considerably higher than the conventional 1.8-2 Gy are required to generate high enough levels of pro-inflammatory cytokines and superior anti-tumor responses. Based on our experience with clinical and pre-clinical tumor models, we hypothesize that pre-operative, prostate SBRT with 3 fractions of 8 Gy given over a relatively short time will lead to measurable immunological changes, locally and systemically. Understanding these changes could inform the use of immunomodulatory therapies in locally-advanced as well as metastatic prostate cancer. Unfortunately, the same pro-inflammatory conditions may drive reprogramming towards a more resistant cancer stem cell phenotype that could increase the likelihood of recurrence in high-risk patients. The balance between these forces and their correlation, if any, in individual high-risk patients will be investigated.

The translational component of this trial seeks: 1. To investigate the radiobiology of SBRT in prostate cancer using resected prostate tumor tissue, and 2. To evaluate the nature of the immune response to prostate cancer generated by SBRT. These aims are included within the secondary objectives of this trial.

### **Scientific impact**

RT causes genotoxicity in irradiated tissue, which is a primary cause of cancer cell killing (21). More recent evidence suggests that additional radiation-induced pathways are at play which drive immune recognition and tumor-immune eradication with potentially systemic consequences, especially after high dose per fraction RT (6–8). The promising synergy between RT and the immune system is underscored by a multitude of ongoing clinical trials that combine local irradiation with systemic immunomodulatory therapeutics. Translational studies correlating such systemic and intratumoral responses using freshly irradiated tissue, however, are extremely rare. Laboratory studies suggests that the doses used in prostate SBRT are close to the optimal fraction sizes to generate such measurable immunological changes. Therefore, this pre-operative prostate SBRT trial offers a unique opportunity to study the radiobiology of SBRT in the clinic, one that simply cannot be ignored.

Another level of complexity arises from the fact that RT may induce markers of EMT and neuroendocrine differentiation in prostate and other cancers, potentially promoting treatment resistance (22,23). If prostate radiotherapy drives such de novo transformations above what exists anyway, then strategies targeting these pathways would be particularly effective when combined with radiation. What's more, the hypothesis is that EMT transformations are promoted by pro-inflammatory conditions, which would suggest an alternative, and less favorable outcome for high-risk patients after receiving SBRT. Resolving the relative importance of EMT viz-a-viz immune system activation in individual patients is a novel and important long-term goal of this study. It will generate insight by studying both EMT and pro-inflammatory and immune SBRT-induced changes within the radiation-damaged microenvironment in vivo using IHC and transcriptomics. Currently, these changes are largely unknown. Therefore, we believe the correlative genomic analyses we have proposed would, at minimum, be hypothesis generating for future investigations with high translational impact.

### **Study design:**

This is a single arm, Phase I feasibility study of SBRT followed by prostatectomy within 4 weeks for patients with prostate cancer at high risk of local failure after prostatectomy. A patient is considered to have completed treatment if they received the prescribed radiation and undergo prostatectomy within 4 weeks of completing radiotherapy.

NUMBER OF PATIENTS;

12 patients in 3 years with recruitment at UCLA Jonsson Comprehensive Cancer Center

### **Objectives:**

**Primary Objective:** To assess feasibility of pre-operative SBRT in prostate cancer patients at high risk for recurrence after prostatectomy. We consider the trial feasible when the estimated treatment completion rate for an enrolled patient is 75%. A patient is considered to have completed treatment if they received the prescribed radiation and undergo prostatectomy within 4 weeks of completing radiotherapy.

#### **• Secondary Objectives:**

- To assess safety and acute toxicity of SBRT followed by prostatectomy. This will be based on CTCAE version 4.0 and patient reported quality of life (EPIC and IPSS questionnaires).
- Investigation of the radiobiology of SBRT in prostate cancer using resected prostate tumor tissue. For the correlative genomic analyses, prostate lesions at the time of prostatectomy will be processed for RNA and exome sequencing and compared to existing sequencing data for localized prostate cancers. We will utilize both supervised and unsupervised analyses of

- Pathway activation from RNA-seq data sets in order to determine which pathways are enriched after irradiation.
- Evaluation of the nature of the immune response to prostate cancer generated by SBRT.
    - Systemic immune response. Blood that is collected pre SBRT, between 0 and 4 weeks after SBRT, and at 3 and 6 month intervals after SBRT will be assessed as follows: PBMCs will be isolated over Ficoll-gradients and stored frozen until analysis. Lymphoid and myeloid subset phenotyping will be assessed by antibody staining and multi-color flow cytometry (LSR-Fortessa, BD). Circulating cytokines, PGE2, prostate-tumor specific antibodies, HMGB-1 protein and the tryptophan/kynurenine ratio in plasma will be quantified by ELISA. Tumor-specific CD4 and CD8 T cell activities to known HLA-matched, immunodominant, tumor-associated antigens will be assessed ex vivo by IFN  $\gamma$  -ELISPOT and dextramer staining. The tumor antigens of choice will include PSA and PSMA.
    - Local immune response. The immune response at the tumor site will be visualized through immunohistochemistry (IHC), with particular focus on T cells (CD3+), T regulatory cells (CD4+ CD25hi), tumor infiltrating myeloid-derived suppressor cells (CD11b+ Gr-1+ CD15+) and tumor-associated macrophages (CD11b+F4/80+). Levels of CSF1/CSF1R, tumor MHC I, PD-1 and PD-L1 are also of interest as are markers for EMT (vimentin, N-cadherin, E-cadherin), for neuroendocrine differentiation (chromogranin A, neuron specific enolase), AR protein and p53. Comparisons will be made to pre-treatment biopsy material when possible and to tissue microarrays of non-irradiated prostatectomy specimens.

## Eligibility Criteria

- Histologically confirmed primary non-metastatic adenocarcinoma of the prostate
- Patient desires and is medically fit to undergo prostatectomy
- Age  $\geq$  18
- KPS  $\geq$  70
- Patients on ADT are allowed
- For confirmation of high risk local failure status, patients will have any one of the following:
  - CT or MRI demonstrating SVI or EPE within 1 year of enrollment into the study
  - Pre-biopsy PSA  $\geq$  20
  - Gleason score 7-10 (Gleason 7 must be 4+3), presence of any Gleason 5 (even if a tertiary score) as determined at diagnostic biopsy

- Gleason score 7 and >50% of biopsy cores positive for prostate cancer
  - Clinical stage  $\geq$  T3 (staging by imaging acceptable)
- An image-guided biopsy (via Artemis Ultrasound with MRI co-registration) is encouraged but not required if not performed as standard of care biopsy

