**OUTCOME MEASURES**

**Primary objective, feasibility:** A patient is considered to have completed treatment if they received the prescribed radiation dose of 24 Gy delivered in 3 fractions of 8 Gy within a span of 2 weeks and subsequently undergo prostatectomy within 4 weeks of completing radiotherapy.

**Secondary objective, safety and acute toxicity:** Patients will be evaluated during RT, prostatectomy, and at intervals of 3 months following completion of treatment for one year. At each visit, patients will complete the EPIC and IPSS questionnaires and will be assessed for CTCAE v4 toxicities.

**Secondary objective, correlative studies:** Assessments of the systemic immune response will utilize blood that is collected pretreatment, after completion of SBRT, and at 3 and 6 months post treatment completion. The local immune response (intratumoral) will utilize the resected prostatectomy specimen, pre-treatment biopsies, and archived tissue arrays of prostatectomy specimens that did not undergo RT. RNA- and exome-sequencing of irradiated prostate tumors will utilize the resected prostatectomy specimens, which will be compared to existing sequencing analyses of localized prostate cancers (TCGA) matched for histology and Gleason grade.

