**Measurements of serological markers (secondary objective).** Circulating cytokines, PGE2, prostate-tumor specific antibodies, HMGB-1 protein and the tryptophan/kynurenine ratio in plasma will be quantified by ELISA. Tumor-specific CD4 and CD8 T cell activities to known HLA-matched, immunodominant, tumor-associated antigens will be assessed ex vivo by IFN $\gamma$ -ELISPOT and dextramer staining. The tumor antigens of choice will include PSA and PSMA. A repeated measures analysis of variance will be used to assess differences in these serological markers over time. In addition to the overall time effect in the ANOVA model, we plan to test specific contrasts

between serological markers pre-treatment (baseline) and the first measurement post SBRT (pre surgery), where we anticipate to observe an increase in circulating tumor-specific CD4 and CD8 T cell activity.

Multivariate profile analyses may be used when patterns for various markers emerge. These statistical analyses will be performed using IBM SPSS Statistics for Windows, Version 20.0. (Armonk, NY) statistical software.

**Measurements of intra-tumoral and intra-prostatic markers (secondary objective).** The immune response at the tumor site will be visualized through immunohistochemistry (IHC), with particular focus on T cells (CD3+), T regulatory cells (CD4+ CD25hi), tumor infiltrating myeloid-derived suppressor cells (CD11b+ Gr-1+ CD15+) and tumor-associated macrophages (CD11b+F4/80+). Levels of CSF1/CSF1R, tumor MHC I, PD-1 and PD-L1 are also of interest as are markers for EMT (vimentin, N-cadherin, E-cadherin), for neuroendocrine differentiation (chromogranin A, neuron specific enolase), AR protein and p53. IntMax (scale of 0-300) = (% of positive tumor cells [scale of 0-100]) X (intensity of staining based on 0-3 scale [scale of 0-3]) will be assessed for each marker. Comparisons in markers will be made between: 1- post SBRT prostatectomy specimens vs biopsy material pre-SBRT; and 2- post SBRT prostatectomy specimens vs archival tissue of prostatectomy specimens (that did not undergo RT).

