For comparison between post SBRT prostatectomy specimens and biopsy material pre-SBRT, average IntMax will be compared using a paired t-test or Wilcoxon signed-rank test (if the IntMax scores do not follow a normal distribution). For comparison between post SBRT prostatectomy specimens and archived material, average IntMax will be compared using a t-test or Wilcoxon rank-sum test (if the IntMax scores do not follow a normal distribution).

**RNA and DNA exome sequencing (secondary objective).** Quality control will be performed on the raw sequence data from RNA-seq experiments, which contain multiple short-read sequences with Phred quality score information using FastQC and FASTX-Toolkit. Bowtie2 will be used to align reads, which will then be mapped to the reference genome by TopHat2. Raw reads from exome sequencing will be aligned via BWA and converted to BAM format, and processed with the Genome Analysis Toolkit software package. Comparisons will be made to existing sequencing data (TCGA) for localized prostate tumors matched for histology and Gleason grade. Functional annotation will be performed using Gene Ontology, KEGG, and Reactome.

**Stopping Rules for Toxicity.** Prior studies evaluating RT prior to prostatectomy demonstrate safety of pre-operative RT at doses of up to 54 Gy in 30 fractions (12). It is anticipated that toxicity in this study will be low because our dose is selected based on the prior studies.

Nevertheless, our trial will be stopped for toxicity if any treatment related toxicity of CTCAE v4.0 grade 3 or above is observed in more than two subjects during the study

period in the following categories: gastrointestinal, urinary, with the exception of temporary use of a catheter and urinary incontinence, which can occur after prostatectomy in the absence of radiotherapy.

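### Patients on ADT may enrol, but the exploratory tissue comparisons ignore ADT, so differences in AR protein and related readouts could be ADT effects credited to SBRT

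*Combined protocol and SAP*

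**What the plan says.** The Eligibility Criteria of the combined protocol and SAP list "Patients on ADT are allowed" without limiting agent, start date, duration or number of such patients. The Study design section plans "12 patients in 3 years with recruitment at UCLA Jonsson Comprehensive Cancer Center", in a single arm, so there is no concurrent unirradiated group.

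Three comparisons use tumour tissue (OUTCOME MEASURES and STATISTICAL CONSIDERATIONS):

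- **Specimen against pre-SBRT biopsy.** The immunohistochemistry score is compared within patients, by a paired t-test or its signed-rank alternative. The Secondary Objectives add that biopsy material is used only where possible.
- **Specimen against archive.** The contrast is "post SBRT prostatectomy specimens vs archival tissue of prostatectomy specimens (that did not undergo RT"). The only stated selection criterion is absence of radiotherapy, and the test is an unadjusted two-sample t-test or rank-sum test.
- **Sequencing against TCGA.** "Comparisons will be made to existing sequencing data (TCGA) for localized prostate tumors matched for histology and Gleason grade".

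The immunohistochemistry readouts include markers "for neuroendocrine differentiation (chromogranin A, neuron specific enolase), AR protein and p53". Serum markers are handled separately, by repeated-measures analysis of variance with a contrast of baseline against the first post-SBRT draw.

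No comparison restricts, matches, stratifies or adjusts for ADT, and no ADT-naive sensitivity analysis is planned.

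**The concern.** The tissue work is meant to show what radiation does to the tumour: the Secondary Objectives look for pathways enriched after irradiation, and the Scientific impact section asks whether radiotherapy drives transformation beyond what is already there. Androgen deprivation acts on the androgen-receptor axis by definition, and AR protein is a named readout. A patient who starts ADT between biopsy and surgery may change on that marker even if SBRT does nothing. An ADT-treated specimen set beside ADT-free archival or TCGA tissue may differ for the same reason. The plan already matches TCGA on two variables, so it accepts that comparability matters, yet it leaves out a treatment it expressly permits. What is at stake is the attribution of an AR, neuroendocrine or pathway signal that the protocol hopes will guide later work.

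**Working it through.** The plan states no power, alpha or effect size for the marker tests, so there is no figure of its own to reproduce. The check has two parts.

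**1. Exposure, comparison by comparison**

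- *Archive and TCGA.* The ADT status of the comparators is neither specified nor matched. Any imbalance between the 12 trial patients and the comparators goes straight into the difference. This is the greatest exposure, and it carries more weight because biopsy pairs may be incomplete.
- *Biopsy pairs.* ADT that is the same at biopsy and surgery largely cancels. The comparison is exposed only through patients whose ADT status changed in between.
- *Baseline against first post-SBRT serum draw.* This too is within-patient, so stable ADT largely cancels.
- *Primary endpoint.* Completion of treatment uses no marker, so it is unaffected.

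**2. Illustrative size**

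Input from the documents: n = 12. Assumptions, none of them in the documents: k of the 12 patients carry an ADT effect of d SD on a marker; the true SBRT effect is zero; two-sided 5% t-tests; all 12 pairs are available; the archive holds 50 ADT-free specimens. For the pairs, d is in SDs of the within-patient difference and k counts patients who started ADT between biopsy and surgery. For the archive, d is in SDs between patients and k counts patients on ADT at surgery.

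Spurious mean shift = (k/12) × d. At the low end this is (2/12) × 0.5 = 0.083 SD; at the high end, (6/12) × 1.5 = 0.75 SD. Simulated false-positive rates (100,000 runs per cell):

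| k of 12 | d (SD) | Shift (SD) | Paired t | Against 50 archival |
|---|---|---|---|---|
| 0 | any | 0 | 5% | 5% |
| 2 | 0.5 | 0.083 | 5.4% | 5.6% |
| 2 | 1.0 | 0.167 | 6.4% | 7.6% |
| 2 | 1.5 | 0.250 | 7.6% | 10.7% |
| 4 | 0.5 | 0.167 | 7.6% | 8.0% |
| 4 | 1.0 | 0.333 | 13.6% | 16.4% |
| 4 | 1.5 | 0.500 | 20.1% | 30.0% |
| 6 | 0.5 | 0.250 | 11.2% | 11.6% |
| 6 | 1.0 | 0.500 | 26.8% | 31.7% |
| 6 | 1.5 | 0.750 | 45.0% | 59.1% |

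The signed-rank alternative does not remove the problem. For the pairs at 1.0 to 1.5 SD it gives 11–17% with 4 of 12 and 23–39% with 6 of 12.

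**3. What a restricted analysis can bear**

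Power of the paired t-test for a true 1 SD SBRT effect (noncentrality √n × 1) is 88% at n = 12, 51% at n = 6 and 29% at n = 4. With 5 pairs the smallest two-sided signed-rank p-value is 2 × (1/2)^5 = 0.0625, so 5% significance cannot be reached.

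**The case against.** The strongest reply is that this is a conditional gap in an exploratory objective. The protocol puts its particular focus on T cells and myeloid cells and lists the AR, neuroendocrine and EMT markers as additional interests. It describes the genomic work as hypothesis generating at minimum. The documents do not say how many patients will be on ADT or how far ADT moves any marker, and at 2 of 12 and 0.5 to 1.0 SD the inflation is small. All of this stands, and it limits the weight of the point. It does not remove it: exploratory status excuses low power, but not a known and recordable confounder in a comparison meant to isolate radiation.

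Three stronger readings are tempting, and the documents do not support them.

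- A reader might infer that the immune and serum results are equally compromised. The mechanism is the androgen axis, the documents offer nothing that links ADT to the immune markers, and the main serum contrast is within-patient.
- A reader might infer that the trial's main translational conclusion is biased. The affected markers are not its main focus.
- A reader might infer that the data needed are already collected at every visit. The Table of Study Assessments records concomitant medications at pre-study, 0–4 weeks post-SBRT and months 3, 6, 9 and 12, with no entry in the pre-SBRT, SBRT or prostatectomy columns. The diagnostic biopsy may also precede the pre-study record.

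**Conclusion.** The point holds for the three tissue comparisons. Followed as written, the plan can credit to SBRT a difference in AR protein, or in related neuroendocrine or pathway readouts, that ADT produced. Exposure is greatest against archive and TCGA; for the biopsy pairs it depends on a change of ADT status between biopsy and surgery. The false-positive rate is about 5% to 45% for the pairs and about 6% to 59% against 50 ADT-free archival specimens. These are illustrations that rest wholly on the assumed ADT share, ADT effect and archive size, and the true size is unknown. That ADT affects AR signalling follows from what it is; an effect on the neuroendocrine and pathway readouts is a premise the documents do not quantify. The feasibility conclusion is not touched. The point is worth acting on because the remedy is cheap, but it does not threaten the trial.

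**What to change.** In STATISTICAL CONSIDERATIONS, with one matching data item:

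1. Code ADT status at biopsy and at surgery from the medical history and concomitant-medication records. Capture ADT start and stop dates explicitly, since the assessment table has no medication entry at surgery.
2. For the archival and TCGA comparisons, add ADT exposure to the matching variables where comparator status is known. Where it is not, repeat the comparison in patients who are ADT-naive at surgery, noting that this removes ADT from the trial side only.
3. Repeat the paired immunohistochemistry comparison in patients with the same ADT status at both times.
4. Report results descriptively by ADT status, as sensitivity analyses. State that a change seen only in ADT-exposed or ADT-discordant patients cannot be attributed to SBRT alone.

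Do not require statistical significance in the restricted subset. The power figures above show that such a rule would discard real SBRT effects.

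The cost is one added data field, a few lines of text and one further run per comparison. The restricted sets will be small and their estimates imprecise. Eligibility and treatment are unchanged.
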